4.1.6 Adjusted Hazard Ratios

The adjusted hazard ratios and 95% CIs will be estimated using weighted Cox regression models. Hazard ratios will be adjusted for possible confounding effects using overlap weighting (Section 4.1.5). This will be conducted in SAS using PROC PHREG with the WEIGHT statement. Normalized weights will be used for the weighted Cox models. The normalized weights add up to the sample size, so that the estimated covariance matrix of the parameter estimators is invariant to the scale of the weights. To account for the fact that the weights are estimated, a robust, sandwich-type variance estimator will be used to calculate 95% CIs. This will be conducted by using the COVSANDWICH option in the PROC PHREG procedure in SAS. Adjusted hazard ratios will be reported as point estimates with 95% CIs.

Time-dependent exposure covariates will be included if violation of the proportional hazards assumption is identified in the unweighted Cox model (described in Section 4.1.4.).

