9.7.1.3.3 Estimation of confounder-adjusted effect measures

The adjusted hazard ratios and 95% CIs for outcomes between exposure groups will be estimated using weighted Cox regression models with effects for exposure status and interaction with site (as appropriate). Time-dependent exposure covariates will be included if violation of the proportional hazard assumption is identified in the unweighted Cox model (described in Section 9.7.1.3.1). Hazard ratios will be adjusted for possible confounding effects using overlap weighting (Section 9.7.1.3.2). If breastfeeding status, postpartum timing, or IUD type are not included within a propensity score (as independent variables when not the dependent variable), then a separate Cox model also including these variables as covariates will be developed. Adjusted hazard ratios will be reported as point estimates with 95% CIs. For any models including time-dependent exposure covariates, separate adjusted hazard ratios will be reported for the estimates of the effect of the exposure over time.

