4.1.4 Crude Hazard Ratios

Crude hazard ratios will be estimated using Cox regression models. These crude hazard ratios will be calculated for each outcome without adjustment for covariates. All crude hazard ratios will be reported as point estimates with 95% CIs.

The proportional hazards assumption between each exposure-outcome pairing will be assessed using visual examination of hazard functions, log-log survival curves, and goodness-of-fit testing using Schoenfeld residuals (Kleinbaum and Klein, 2012). Parallel hazard function and log-log survival curves for exposure groups (i.e., the vertical distance between exposure groups is constant) would indicate that the assumption of proportional hazards is met. The hazard function and log-log plot will be generated using the PLOTS=(H LLS) option in the PROC LIFETEST procedure in SAS. The goodness-of-fit global correlation test based on Schoenfeld residuals will be conducted using the ZPH(GLOBAL) option in the PROC PHREG procedure in SAS. A test with $P < 0.05$ will indicate that the proportional hazards assumption does not hold. If both visual examination and the global correlation test suggest nonproportional hazards, the time-dependent exposure covariate will be included in crude and adjusted hazard ratio models by fitting interaction terms with continuous or categorical time (Paul, 1995). The form of the interaction terms will be determined after reviewing the plots of hazard functions and log-log survival curves. An example SAS program code follows, where *brstime* is the time-dependent exposure covariate created with the programming statement in the PHREG procedure as an exposure-by-time interaction:

```
PROC PHREG DATA=start;
  CLASS brstfeed;
  MODEL personyr * outcome (0) = brstfeed brstime / TIES=EFRON;
  brstime = brstfeed * (personyr > 0.5); /* use 0.5 as an example*/
RUN;
```

For any models including time-dependent exposure covariates, separate hazard ratios will be reported for estimates of the effect of the exposure over time.

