Programming note 4: Site (data source) will be shown only for the pooled table, not for the site tables.

Programming note 5: Results by IUD type will be presented only for the pooled table, not by site.

**Table Layout 2.1. Hazard Ratios of Uterine Perforation for Breastfeeding Status;
 Analysis Set: Breastfeeding Status Available, First IUD Insertion;
 Database: Pooled and by Site**

Site	Breastfeeding Status	Events	Insertions	Person-years	Crude HR (95% CI)	Adjusted	
						HR (95% CI)	P Value
Pooled	Yes	XX	XX	XXX,XXX.X	x.xx (x.xx, x.xx)	x.xx (x.xx, x.xx)	0.XXXX
	No	XX	XX	XXX,XXX.X	1.00 (Reference)	1.00 (Reference)	-
KPNC	Yes	XX	XX	XXX,XXX.X	x.xx (x.xx, x.xx)	x.xx (x.xx, x.xx)	0.XXXX
	No	XX	XX	XXX,XXX.X	1.00 (Reference)	1.00 (Reference)	-
KPSC	Yes	XX	XX	XXX,XXX.X	x.xx (x.xx, x.xx)	x.xx (x.xx, x.xx)	0.XXXX
	No	XX	XX	XXX,XXX.X	1.00 (Reference)	1.00 (Reference)	-
KPWA	Yes	XX	XX	XXX,XXX.X	x.xx (x.xx, x.xx)	x.xx (x.xx, x.xx)	0.XXXX
	No	XX	XX	XXX,XXX.X	1.00 (Reference)	1.00 (Reference)	-
RI	Yes	XX	XX	XXX,XXX.X	x.xx (x.xx, x.xx)	x.xx (x.xx, x.xx)	0.XXXX
	No	XX	XX	XXX,XXX.X	1.00 (Reference)	1.00 (Reference)	-

CI = confidence interval; HR = hazard ratio; IUD = intrauterine device.

Note: Crude HRs were estimated from five Cox models using pooled data or within each site. Adjusted HRs were estimated from two Cox models weighted using overlap weights. The adjusted HRs by site were estimated from the Cox model including exposure, site, and site-by-exposure interaction (type 3 group test for interaction: $P = 0.xxxx$); the overall adjusted HR (reported only if the interaction is not significant) was estimated from the Cox model including exposure and site.

Note: The P value is from the Cox model for the test of the null hypothesis that the adjusted HR equals one.

Note: The proportional hazards assumption was tested using the global correlation test based on Schoenfeld residuals with the pooled data ($P = 0.xxxx$).

Generated using `xxxx.sas` on `xxxxxxx`.

Programming note 1: The pooled adjusted HR and related footnote will be shown only if the interaction term is not statistically significant ($P > 0.05$).

Programming note 2: If the proportional hazards assumption is violated, time-dependent exposure covariates will be included in Cox models. The table above will be expanded to include separate hazard ratios for the effect of exposure over time.

Programming note 3: For tables that include results by IUD type, only pooled results will be presented, not by site.

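### Proportional hazards is checked only in the crude Cox model, never in the overlap-weighted model that gives the primary hazard ratios

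*SAP*

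**What the plan says.** SAP 4.1.4 defines the model on which proportional hazards is assessed: "These crude hazard ratios will be calculated for each outcome without adjustment for covariates". The tools are hazard and log-log plots and a global Schoenfeld-residual test, for which P < 0.05 "will indicate that the proportional hazards assumption does not hold". The trigger requires agreement: "If both visual examination and the global correlation test suggest nonproportional hazards", then "the time-dependent exposure covariate will be included in crude and adjusted hazard ratio models by fitting interaction terms with continuous or categorical time". Separate hazard ratios over time are then reported.

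SAP 4.1.6 repeats the link for the weighted model: "Time-dependent exposure covariates will be included if violation of the proportional hazards assumption is identified in the unweighted Cox model". Protocol 9.7.1.3.3 matches it: "Time-dependent exposure covariates will be included if violation of the proportional hazard assumption is identified in the unweighted Cox model". Protocol 9.7.1.3.1 also carries a crude finding into both models.

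SAP 6.2.1 attaches the assessment to the crude hazard ratios. It takes the primary result from the weighted Cox model, with one two-sided test of the overall adjusted log hazard ratio when the site interaction is not significant. The notes to Layouts 2.1 and 2.2 in SAP 9.5 say "The proportional hazards assumption was tested using the global correlation test based on Schoenfeld residuals with the pooled data" and do not mention weights. I found no place in either document where the assumption is examined in the weighted model.

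**The concern.** The model that is tested is not the model that is reported. How the crude hazard ratio behaves over time reflects both the exposure effect and any confounding that changes over time. Overlap weighting is there to remove measured confounding, but the decision about time terms is taken on data from which it has not been removed.

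Two errors can follow:

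- **Unneeded split.** The adjusted hazard ratio is constant, the crude one is not, and exposure-by-time terms enter the weighted primary model. The estimate is then divided into periods, with few events in each, and SAP 6.2.1 does not say which estimate carries the primary test.
- **Missed change.** The adjusted hazard ratio changes over time, confounding flattens the crude one, and a single weighted hazard ratio is reported as if it were constant.

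Follow-up has no maximum other than the stated stopping events, so the assumption may have to hold over several years.

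**Working it through.** **Inputs from the documents.** Protocol 9.5 gives 225,000 first insertions, 60,000 with breastfeeding status, a risk of 1.3 per 1,000 and allocations of 5:20:5:70 and 60:40. Expected events for objective 2 are 225,000 × 0.0013 = 292.5.

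**The plan's own figures.** Schoenfeld power is Φ(√(d·p(1−p))·ln HR − 1.96). At HR 2.0:

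| Comparison | Events d | Exposed share p | Computed | Table 4 |
|---|---|---|---|---|
| Breastfeeding | 78.0 | 0.60 | 85.1% | 85% |
| ≤ 6 weeks | 219.4 | 5/75 | 72.6% | 73% |
| > 6 to ≤ 14 weeks | 263.2 | 20/90 | 99.7% | > 99% |

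These reproduce and are not in dispute.

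**Why the two checks can differ.** Take one binary covariate with prevalence p1 in the exposed and p0 in the referent, and hazard ratio g(t). With events this rare,

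crude HR(t) = adjusted HR(t) × [1 − p1 + p1·g(t)] / [1 − p0 + p0·g(t)].

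Overlap weights that balance the covariate make the second factor 1. If g is constant, that factor is constant too, and crude and adjusted hazard ratios are proportional or non-proportional together. They part only if g changes over time or, by a route not quantified here, if censoring changes the mix of women at risk. The prevalences, the values of g and the two-period split below are assumptions.

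**All of objective 2, 292 events, 3-df test, half the baseline events early.** The ranges span two forms of test: a rank-time Schoenfeld-type score test and a two-period exposure-by-time Wald test.

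| Covariate, exposed vs referent | g early, late | Crude/adjusted factor, early | Crude test rejects | Weighted test rejects |
|---|---|---|---|---|
| 40% vs 10%, adjusted HR constant | 3, 1 | 1.8/1.2 = 1.50 | 18-20% | 3-7% |
| 10% vs 40%, adjusted HR constant | 3, 1 | 1.2/1.8 = 0.67 | 17-20% | 3-7% |
| 20% vs 40%, adjusted HR constant | 3, 1 | 1.4/1.8 = 0.78 | about 9% | about 3% |
| Constant-effect covariate | 3, 3 | same early and late | about 4% | 4-5% |
| 10% vs 40%, adjusted HR 2 then 1 | 4, 1 | 1.3/2.2 = 0.59 | 4-5% | 33-42% |

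In the last row the crude hazard ratio is 2 × 0.59 = 1.18 early and 1.00 late, so it looks nearly proportional.

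**Pairwise check, > 6 to ≤ 14 weeks vs > 52 weeks, 263 events, 70% of the baseline hazard early.**

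- Adjusted HR constant at 2.0, covariate 50% vs 15%, g 4 then 1. Crude HR is 2 × 2.5/1.45 = 3.45 early and 2.00 late. Crude test 39%, weighted 5%.
- Milder: 35% vs 20%, g 3 then 1. Crude HR is 2 × 1.7/1.4 = 2.43 early and 2.00 late. Crude 9%, weighted 4%.
- Masked: adjusted HR 3.45 then 2.00, covariate 15% vs 50%, g 4 then 1. Crude HR is 3.45 × 1.45/2.5 = 2.00 in both periods. Crude 5%, weighted 28%.
- Constant g = 2, covariate 50% vs 15%. Crude HR is 2 × 1.5/1.15 = 2.61 in both periods. Both tests about 5%.

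**Smaller comparisons.** The first pairwise scenario gives 15% crude and 4% weighted for ≤ 6 weeks (219 events), and 13% and 4% for breastfeeding (78 events). In the masked scenarios the weighted test for ≤ 6 weeks detects only about 6-7%.

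**The case against.** **The premise is conditional.** An imbalanced covariate is not enough; its effect must change over follow-up, and neither document shows that one does. Protocol 9.7.1.2.1 anticipates a changing outcome risk over time, but a Cox model allows the baseline hazard to change freely. That sentence is not evidence of a changing hazard ratio. This stands, so how often the problem would arise is unknown.

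**A reader might infer that crude confounding forces time-split results.** It does not. SAP 4.1.4 requires the plots and the test to agree, and the simulations cover the test alone. The firm part is what follows once both agree: "the time-dependent exposure covariate will be included in crude and adjusted hazard ratio models".

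**A reader might infer a much larger effect from breastfeeding.** The case is about 60% breastfeeding in the postpartum groups and none in the referent, with Table 2's relative risk of 3.3 waning to 1.0. That gives crude rejection as high as 70%, but it says little about this rule. The referent propensity of breastfeeding women is then zero, so w = 1/(e_k·Σ1/e_j) gives each of them weight zero. Expected postpartum events are 67,500 × [0.5 × (0.4 + 0.6 × 3.3) + 0.5] × 292.5/271,575 ≈ 123, where 271,575 = 114,075 + 157,500 is the weighted total of insertions. Only 27,000 × 292.5/271,575 ≈ 29 of these remain after weighting. The weighted test is then answering for a different population, which is a positivity matter. Table 2's figure is also a 12-month relative risk with no time pattern. I place no weight on this scenario.

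**The harm is limited, and partial safeguards exist.** If the adjusted hazard ratio is constant, period-specific weighted estimates lose precision but are not biased. The note in Layout 2.1 expands the table. Crude 1- and 5-year cumulative incidence and weighted rate ratios at 1 and 5 years (36-week cut) are planned. This stands, although none of these checks the weighted hazard ratio of either primary objective for constancy.

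**A weighted check has low power in small groups.** This also stands and shapes the fix.

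**Conclusion.** The point holds in a limited form. The proportional hazards rule for the primary weighted models rests on a different model, and nothing in the plan examines the weighted one. With ordinary covariates whose effects wane, the crude test alone raises a false signal about 9-20% of the time, against about 3-7% with weights. Where confounding masks a true adjusted change from 2 to 1, it detects about 5%, against 33-42%. These figures rest on assumed prevalences and waning, on two periods and on the planned event count. The crude rates are upper bounds on switching, and a constant-effect covariate causes no problem.

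The documents do not support a claim that the primary estimate will be biased, or that a time split is likely. The rule applies equally to objective 1 and the secondary adjusted hazard ratios. Objective 2 is the most exposed, because its referent includes women with no recorded delivery in the past 52 weeks. No sample size or power figure changes.

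**What to change.** 1. In SAP 4.1.4 and Protocol 9.7.1.3.1, keep the crude check for the crude hazard ratio, and stop a crude finding from adding time terms to the adjusted model.
2. In SAP 4.1.6 and Protocol 9.7.1.3.3, assess proportional hazards for each adjusted hazard ratio in the overlap-weighted model. Use weighted log-log curves and an exposure-by-time term (one per exposure level), tested jointly with the COVSANDWICH variance already planned. Base the adjusted model's time-dependent terms on that assessment.
3. Give both P values, crude and weighted, in the notes to Layouts 2.1 and 2.2. Add to Layout 2.2 the expansion note that only Layout 2.1 now carries.
4. Always report the overall weighted hazard ratio and its P value beside any period-specific ones.
5. State that a non-significant weighted test is not proof of proportionality, especially for ≤ 6 weeks.

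The cost is a wording change in both documents and one extra model run per exposure-outcome pair, with no new data. The drawback is the weighted check's low power in the small groups, which is why items 4 and 5 belong with it.

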4.1.7 Crude IRR

The crude IRR will be calculated as the crude incidence rate in the exposed divided by the crude incidence rate in the unexposed.

$$IRR = \frac{\text{Incidence rate in the exposed}}{\text{Incidence rate in the unexposed}} = \frac{E_1/Y_1}{E_2/Y_2}$$

where E_1 is the number of incident outcomes occurring during person-years at risk in the exposed group, Y_1 is the total person-years at risk in the exposed group, E_2 is the number of incident outcomes occurring during the person-years at risk in the unexposed group, and Y_2 is the total person-years at risk in the unexposed group.

The 95% CI of the crude IRR will be calculated using a Poisson distribution and test-based methods defined in Sahai and Khurshid (1996). The lower and upper bounds of the 95% CI will be calculated as follows:

$$IRR_{LB} = \left(\frac{Y_2}{Y_1}\right) \left(\frac{E_1}{E_2 + 1}\right) \frac{1}{F_{0.025, 2(E_2+1), 2E_1}}, IRR_{UB} = \left(\frac{Y_2}{Y_1}\right) \left(\frac{E_1 + 1}{E_2}\right) F_{0.025, 2(E_1+1), 2E_2}$$

where $F_{0.025, \nu_1, \nu_2}$ represents the 2.5th percentile of the F distribution with ν_1 and ν_2 degrees of freedom.

All crude IRRs will be reported as point estimates with 95% CIs.

4.1.8 Adjusted IRR Via Weighting

The IRR will be adjusted for possible confounding effects via weighted estimation of the rates using overlap weights (Section 4.1.5) derived from the same propensity score models as those developed for adjustment of the hazard ratios. The adjusted IRR will be calculated as the weighted incidence rate in the exposed divided by the weighted incidence rate in the unexposed.

$$IRR_w = \frac{\text{Weighted incidence rate in the exposed}}{\text{Weighted incidence rate in the unexposed}} = \frac{E_{w1}/Y_{w1}}{E_{w2}/Y_{w2}}$$

where E_{w1} is the number of weighted incident outcomes occurring during person-years at risk in the exposed group, Y_{w1} is the total weighted person-years at risk in the exposed group, E_{w2} is the number of weighted incident outcomes occurring during the person-years at risk in the unexposed group, and Y_{w2} is the total weighted person-years at risk in the unexposed group.

The 95% CI of IRR_w will be calculated as described in Section 4.1.7 using a Poisson distribution and the number of weighted incident outcomes and weighted person-years.

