There were approximately 325,000 IUD insertions identified during the time frame of the validation/feasibility study (i.e., end date, 30 September 2015), and approximately 65% of those occurred after at least 12 months within the data source. In approximately 90% of IUD insertions, this was the first observed insertion for each woman. Approximately 30% of women were identified as having an IUD inserted within the first 52 weeks postpartum. Based on these results and assumptions—approximately three additional years of data more than the validation study and allowing for a loss of approximately 15% of the insertions due to missing data and the propensity score trimming process (Section 9.7.1.3.2)—the number of first insertions of an IUD available through June 2018 from the four health care systems is anticipated to be approximately 225,000, with breastfeeding status available for approximately 60,000. For the two primary objectives related to the risk of uterine perforation, the power of the study is calculated for differences in the estimated risk of uterine perforation with respect to (1) breastfeeding status at the time of IUD insertion and (2) time interval of the IUD insertion following delivery. The null hypothesis to be tested for primary objective 1 is that the natural logarithm of the adjusted summary perforation hazard ratio for breastfeeding versus not breastfeeding at the time of IUD insertion is equal to 0. Using information from validation study, the expected allocation ratio of breastfeeding versus not breastfeeding is 60:40 for this objective. Three null hypotheses to be tested for primary objective 2 are that the natural logarithm of the adjusted summary perforation hazard ratio for early (i.e., ≤ 6 weeks postpartum, > 6 and ≤ 14 weeks, > 14 and < 52 weeks) versus later (i.e., > 52 weeks) postpartum IUD insertion is equal to 0. Based on information from the validation study, the expected allocation ratio of the corresponding postpartum period categories is 5:20:5:70 for this objective.

Power calculations for the expected number of IUD insertions were performed using PASS 14 software (NCSS, LLC, Kaysville, Utah) for a two-sided test of the hazard ratio (Schoenfeld, 1983). Table 4 indicates the power to detect various hazard ratios at the two-sided $\alpha = 0.05$ significance

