For categorical exposure variables with more than two levels, the propensity scores will be estimated for each patient and exposure level. Consider an exposure variable with K exposure groups ($K > 2$). The propensity score for patient i and exposure k , $k=1, \dots, K$, denoted as e_{ik} , is the probability that a patient will be exposed to exposure k conditional on measured covariates X_i :

$$e_{ik} = \Pr(Z_i=k|X_i), \text{ with } \sum_{k=1}^K e_{ik} = 1$$

The overlap weight for patient i given exposure k is defined as follows:

$$w_{ik} = \frac{1}{e_{ik} \sum_{k=1}^K \frac{1}{e_{ik}}}$$

The overlap weights will be normalized by multiplying the weights by $\frac{n}{\sum_{i=1}^n w_i}$, where n is the total sample size. The extreme weights (min, max), mean, and standard deviation of the normalized weights will be assessed, although extreme weights are not expected to be an issue with overlap weights because the overlap weights are bounded.

The distribution of propensity scores among exposed (e.g., breastfeeding at the time of IUD insertion) and unexposed (e.g., not breastfeeding at time of IUD insertion) patients will be examined using histograms with kernel smoothing to identify the overlapping area. However, all patients will be included in the analysis when applying overlap weights. The overlap weights put the strong focus on those patients with the highest overlap in their propensity scores and therefore avoid the need for trimming the population.

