4.1.10 Adjusted IRD Via Weighting

The IRD will be adjusted for possible confounding effects via weighted estimation of the rates using overlap weights (Section 4.1.5) derived from the same propensity score models as those developed for adjustment of the hazard ratios. The adjusted IRD will be calculated as the weighted incidence rate in the exposed minus the weighted incidence rate in the unexposed.

$$IRD_w = \frac{E_{w1}}{Y_{w1}} - \frac{E_{w2}}{Y_{w2}}$$

The 95% CI of IRD_w will be calculated as described in Section 4.1.9 using the number of weighted incident outcomes and weighted person-years.

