6.2.2.3 Comparing Adjusted IRR and Adjusted IRD

To compare results from this study to those obtained in EURAS-IUD, we will estimate the adjusted IRR and IRD of uterine perforation at 1 year and 5 years of follow-up among women who had a first observed IUD insertion ≤ 36 weeks postpartum versus women who had a first observed IUD insertion > 36 weeks postpartum, including women without recorded delivery within the past 52 weeks (objective 17). Adjusted IRRs and IRDs will be calculated via weighted estimation of the rates using overlap weights as described in Sections 4.1.8 and 4.1.10, respectively.

Using the final analysis datasets after propensity score development and weighting, we will calculate adjusted IRRs and IRDs for the study outcomes. Tables will display the weighted number of outcomes, total weighted person-years, and weighted incidence rates for women who had a first observed IUD insertion ≤ 36 weeks postpartum and for women who had a first observed IUD insertion > 36 weeks postpartum. The adjusted IRRs and IRDs along with 95% CIs will be displayed. Analysis Tables 17.1 will be created for uterine perforation.

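### The adjusted IRR and IRD intervals (objectives 17 and 25) treat overlap-weighted event totals as Poisson counts and so do not have 95% coverage; SAP 4.1.7 also names the wrong F percentile

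*SAP*

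**What the plan says.** Objectives 17 and 25 estimate the adjusted IRR and IRD of perforation and expulsion at 1 and 5 years, for insertion ≤ 36 versus > 36 weeks postpartum. SAP 6.2.2.3 gives comparison with EURAS-IUD as the purpose of objective 17. Table Layout 10 reports results pooled and by site.

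- **IRR (SAP 4.1.8):** the interval "will be calculated as described in Section 4.1.7 using a Poisson distribution and the number of weighted incident outcomes and weighted person-years".
- **IRD (SAP 4.1.10):** the interval "will be calculated as described in Section 4.1.9 using the number of weighted incident outcomes and weighted person-years". Section 4.1.9 is a Wald interval with variance E1/Y1² + E2/Y2².
- **Weights (SAP 4.1.5):** "The overlap weights will be normalized by multiplying the weights by" n/Σw, with n the total sample size. Section 4.1.6 names normalised weights for the Cox models. Sections 4.1.8 and 4.1.10 cite 4.1.5 but do not say whether raw or normalised weights apply.
- **Reporting (SAP 6.2.2.3):** "Tables will display the weighted number of outcomes, total weighted person-years, and weighted incidence rates". No variance method is added there.
- **Hazard ratio, for contrast (SAP 4.1.6):** "To account for the fact that the weights are estimated, a robust, sandwich-type variance estimator will be used to calculate 95% CIs".
- **F quantile (SAP 4.1.7):** F_0.025 "represents the 2.5th percentile of the F distribution".

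Protocol 9.7.1.4.3 and 9.7.1.4.4 promise 95% intervals for the adjusted IRR and IRD but give no variance for the weighted rates.

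**The concern.** The formulas in 4.1.7 and 4.1.9 rest on the variance of a Poisson count equalling its mean. A weighted total E_w = Σwd (d = 1 for an event) has variance Σw²d. The two agree only when every event carries weight 1. If all weights are multiplied by c, IRR_w and IRD_w stay the same, but the planned variances are divided by c.

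The SAP guards against this for the hazard ratio with normalised weights and a sandwich variance. It gives the rate measures no such variance.

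At stake is whether the intervals in the EURAS-IUD comparison mean what they claim. The IRD, which is the absolute-risk measure, is affected most.

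**Working it through.** **Inputs from the documents.** Protocol 9.5 gives 225,000 first insertions and 1.3 perforations per 1,000, so 225,000 × 0.0013 = 292.5 events. It also says "the expected allocation ratio of the corresponding postpartum period categories is 5:20:5:70 for this objective". The ≤ 36-week share is not stated, but it must lie between 25% (≤ 14 weeks) and 30% (≤ 52 weeks). Both ends were used.

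**Assumptions.** Equal, complete 1-year follow-up; about equal total weight in the two groups; known propensity scores.

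**Planning inputs check.** The documents give no power or precision figure for objectives 17 and 25. The same inputs do reproduce Table 4. For 60,000 women at 60:40 and HR 2.0 there are 78 events, and √(78 × 0.6 × 0.4) × ln 2 − 1.96 = 1.04, which is 85.1% power against the stated 85%.

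**One case by hand: share 25%, IRR 2, no propensity spread.** Real events are 117 and 175.5, in 56,250 and 168,750 person-years. Raw overlap weights are 0.75 and 0.25. The normalising factor is 1/(2 × 0.25 × 0.75) = 2.667, so normalised weights are 2.0 and 0.667. Weighted events are then 234 and 117, each over 112,500 weighted person-years.

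- SE(log IRR): claimed √(1/234 + 1/117) = 0.113; true √(1/117 + 1/175.5) = 0.119. Ratio 0.949.
- IRD half-width per 1,000: claimed 1.96 × √(234 + 117)/112.5 = 0.326; true 1.96 × √(117/56.25² + 175.5/168.75²) = 0.407. Ratio 0.802.
- IRR interval around 2.0 by the 4.1.7 formula (correct F tail): unweighted counts 1.57 to 2.54; normalised 1.60 to 2.52; raw 1.38 to 2.94. The data are the same each time; only the scale of the weights differs.

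**Claimed/true SE with normalised weights and no propensity spread:**

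| Share | IRR | Real events | Weighted events | log IRR | IRD |
|---|---|---|---|---|---|
| 25% | 1 | 73.1 / 219.4 | 146.25 / 146.25 | 0.866 | 0.866 |
| 25% | 2 | 117 / 175.5 | 234 / 117 | 0.949 | 0.802 |
| 25% | 3 | 146.25 / 146.25 | 292.5 / 97.5 | 1.000 | 0.775 |
| 30% | 1 | 87.8 / 204.8 | 146.25 / 146.25 | 0.917 | 0.917 |
| 30% | 2 | 135 / 157.5 | 225 / 112.5 | 0.984 | 0.861 |
| 30% | 3 | 164.5 / 128.0 | 274.2 / 91.4 | 1.025 | 0.837 |

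Normalising over the whole sample gives each group a total weight of about n/2. A 25% group is thus credited with twice its real events. With raw weights and no spread, the claimed SE is 1.41 to 1.63 times the true one for the IRR and 1.27 to 1.41 times for the IRD.

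**Simulated coverage of nominal 95% intervals** (4,000 replicates in each of 36 scenarios; share 25% or 30%; IRR 1, 2 or 3; log-risk slope 0.3 per SD where scores vary; F tail corrected):

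| Weights | SD of logit propensity | IRR | IRD |
|---|---|---|---|
| Normalised | 0 | 92-96% | 87-93% |
| Normalised | 1 (c about 0.74) | 89-93% | 85-90% |
| Normalised | 2 (c about 0.87) | 84-87% | 80-85% |
| Raw | all | 98.5-99.9% | 98.5-99.9% |
| Σw²d variance | all | 94-96% | 94-96% |

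A second simulation with 10,000 replicates at IRR 1 and 2 agrees: normalised weights give 83.3-95.3% (IRR) and 80.7-92.5% (IRD).

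**F percentile.** The lower limit in 4.1.7 divides by F and the upper multiplies by F, so both need the upper 2.5% point. SAP 4.1.2 uses lower-tail percentiles, so the literal reading is the document's own convention. On the EURAS-IUD counts in Protocol section 7 (61/43,078 versus 20/18,370, ratio 1.30), the 2.5th percentile gives a lower limit of 2.11 and an upper limit of 0.82. The 97.5th gives 0.77 to 2.28, which equals the exact conditional interval. With 73 versus 219 events in 56,250 and 168,750 person-years the limits are 1.29 and 0.77, against 0.76 to 1.31. The matching wording for Z in 4.1.9 is harmless because of the ±.

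**The case against.** **The scale is largely fixed.** The steps in 4.1.5 normalise the weights before any effect is estimated, so the raw-weight results describe an unlikely reading. This stands as far as it goes. Normalisation fixes the scale but at a value that miscounts both groups' events, and it ignores unequal weights.

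**The IRR error can be small.** With little propensity spread and an IRR of about 2, coverage is close to 95%. This also stands, but it is a coincidence of share and effect size. The IRD covers about 88-91% in the same setting.

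**The largest shortfalls rest on an assumed spread.** The documents give no propensity distribution. Moreover, 36 weeks is not a boundary of the four-category model, so the collapsing rule in 6.2.2.2 and 9.3 does not itself define a ≤ 36-week score. The magnitudes are therefore illustrative. Only 1-year perforation was simulated; the 5-year and expulsion results rest on the same algebra.

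**Most remedies treat the weights as known.** Only the bootstrap re-estimates them, and the Σw²d results used known scores. This bears on the choice of remedy and does not defend the planned interval.

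**The consequence is limited.** These are secondary estimation objectives. The same 36-week contrast is reported as hazard ratios with a sandwich variance (objectives 15 and 22), and reversed F limits would be noticed on first output. All true, and reflected in the verdict.

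**Conclusion.** The concern holds. Followed as written, 4.1.8 and 4.1.10 give intervals that are not 95% intervals. With normalised weights the IRD interval is too narrow in every scenario examined (coverage 80-93%). The IRR interval is too narrow (84-93%) unless propensity scores vary little and the IRR is about 2 or more, where coverage is close to nominal. With raw weights both intervals are far too wide.

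These sizes depend on the assumed ≤ 36-week share, propensity spread, follow-up and known scores. The underlying error does not: Σwd is the wrong variance whatever those values are.

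The F percentile is a wording erratum. It also touches the crude IRR and adds little to the severity. Scope is objectives 17 and 25, pooled and by site. The primary hazard ratios and their tests are not affected.

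**What to change.** In SAP 4.1.8 and 4.1.10, replace the Poisson-based intervals with one of the following, all unaffected by the scale of the weights:

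- a weighted Poisson model with log person-time offset and a sandwich variance by woman;
- Var(E_w) = Σw²d with the delta method for log IRR, and Σw²d/Y_w² summed over the two groups for the IRD;
- a bootstrap by woman that re-estimates the propensity model and weights. This is the only option that fully reflects estimation of the weights.

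In 4.1.7, define F_0.025 as the 97.5th percentile (upper 2.5% point).

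The cost is three SAP sentences and a few lines of code. No new data are needed, point estimates stay the same, and no primary analysis changes.
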